6.11.6. Deaths

The listing of all deaths by patient for all enrolled patients will be provided as part of the SAE listing, regardless of the investigator's or the sponsor's judgment about causality. Each listing will include study ID, investigator ID, patient ID, treatment sequence, treatment group, baseline age, sex, associated AE, first and last dose date for open label insulin lispro and randomized IP, and the event date.

6.11.7. Hypoglycemic Events and Other Adverse Events

The analysis plans for the following adverse events are discussed in Section 6.11.7.1 through Section 6.11.8:

- hypoglycemic events
- systemic hypersensitivity reaction
- infusion site reaction
- malignant neoplasm events

These AE analyses will be similar to the TEAE analyses, refer to Table ITSI.6.5 for the requirement of analysis data for a specific analysis period.

6.11.7.1. Hypoglycemic Events

Hypoglycemia events that occur during the study will be captured using an eCOA diary starting from Visit 2 through Visit 801. Whenever hypoglycemia is suspected, the patient should record the blood glucose value, any associated symptoms, and the treatment administered in eCOA. A

set of events is counted as 1 event in analysis if it consists of an originating event and subsequent continuing events as marked by the patient in eCOA, or the duration between adjacent events is ≤ 30 minutes. The event with the highest severity will be selected for analysis with severity determined in the order of: 1) it is a severe hypoglycemia, 2) it has symptoms of hypoglycemia reported, and 3) it has the lowest blood glucose value. If there are multiple events tied in all 3 aspects, the event with the largest number of non-missing responses to the questions of nocturnal hypoglycemia and postmeal time frame will be selected. If there are still multiple events tied, the latest event (based on data entry time) will be selected.

The following types of hypoglycemia events will be derived in the analysis data sets: documented hypoglycemia, severe hypoglycemia, nocturnal hypoglycemia, probable symptomatic hypoglycemia, and overall hypoglycemia. Only severe hypoglycemia will be collected as AEs and all episodes of severe hypoglycemia will be considered as SAEs. Documented hypoglycemia (including documented symptomatic hypoglycemia, documented asymptomatic hypoglycemia and documented unspecified hypoglycemia) will be based on blood glucose (BG) ≤ 70 mg/dL. In addition, documented clinically significant hypoglycemia with similar criterion as above documented hypoglycemia except for the threshold of BG < 54 mg/dL will be summarized.

Table ITSI.6.6 provides detailed statistical methods for each endpoint related to hypoglycemia. For these analyses, hypoglycemia events prior to the discontinuation (i.e., last dose) of IP will be summarized. Additional analyses for other types of hypoglycemic events not mentioned in the table may be conducted as needed.

A listing of patients with at least 1 severe hypoglycemia reported (as SAE) after randomization (including Visit 801) will be provided.

A list of MedDRA PTs will be used for the narrow search of potential severe hypoglycemia in spontaneously reported AEs. The events identified through the search strategy that are also reported as SAEs will be summarized and compared between treatments. Prescott’s exact test will be used to assess the treatment difference in the proportion of patients with potential severe hypoglycemia.

Table ITSI.6.6. Summary of Analyses for Endpoints Related to Hypoglycemia

Endpoint	Analysis Period	Statistical Method
Rate of hypoglycemic events (per patient per 30 days / year) 
 • All Documented^a • Nocturnal^a • Documented Symptomatic^a • Overall • Non-Nocturnal (or Daytime) (Documented and between waking and bedtime)^a • Probable Symptomatic 	0-4, 0-6, 4-6 weeks	Wilcoxon signed-rank test will be conducted.

Endpoint	Analysis Period	Statistical Method
Incidence of hypoglycemic events 
 All Documented^a Nocturnal^a Documented Symptomatic^a Overall Non-Nocturnal (or Daytime)(Documented and between waking and bedtime)^a Probable Symptomatic 	0-4, 0-6, 4-6 weeks	If there are ≥ 5 patients with at least one event within the specified time period, a generalized linear mixed model with options of the binomial distribution and logit link function with treatment, period, sequence. The within-patient error will be modeled as a compound symmetry without heterogeneous variance-covariance matrix. If the model does not converge, Prescott's exact test will be conducted.
Rate of post-meal hypoglycemic events (per patient per 30 days / year) 
 Documented Symptomatic^a Documented Asymptomatic^a 	≤ 0.5 , ≤ 1 , ≤ 2 , ≤ 4 , > 1 to ≤ 2 and > 2 to ≤ 4 hours after start of a meal within 0-4, 0-6, and 4-6 weeks	Wilcoxon signed-rank test will be conducted.
Incidence of post-meal hypoglycemic events 
 Documented Symptomatic^a Documented Asymptomatic^a 	≤ 0.5 , ≤ 1 , ≤ 2 , ≤ 4 , > 1 to ≤ 2 and > 2 to ≤ 4 hours after start of a meal within 0-4, 0-6, and 4-6 weeks	If there are ≥ 5 patients with at least one event within the specified time period, a generalized linear mixed model with options of the binomial distribution and logit link function with treatment, period, sequence. The within-patient error will be modeled as a compound symmetry without heterogeneous variance-covariance matrix. If the model does not converge, Prescott's exact test will be conducted.
Rate of severe hypoglycemic events (per patient per year / 100 years)	0-4, 0-6, 4-6 weeks	Exposure adjusted rate per year / 100 years (calculated for each patient by total number of events divided by total exposure) will be provided and Wilcoxon signed-rank test will be used for treatment comparison.
Incidence of severe hypoglycemic events	0-4, 0-6, 4-6 weeks	Proportion of patients with severe hypoglycemia will be reported. The treatment comparison will be based on Prescott's exact test.

^a All documented hypoglycemia and the subcategories based on the thresholds of blood glucose ≤ 70 mg/dL and blood glucose < 54 mg/dL will be analyzed, except for post-meal hypoglycemia for which only the threshold of ≤ 70 mg/dL will be applied.

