  - **Nocturnal Hypoglycemia:** any documented hypoglycemic event (including severe hypoglycemia) that occurs between bedtime and waking.
  - **Relative Hypoglycemia (also referred to as Pseudohypoglycemia [Seaquist et al. 2013]):** an event during which typical symptoms of hypoglycemia occur that do not require the assistance of another person, are accompanied by BG  $>$ 70 mg/dL (3.9 mmol/L). Patients may report symptoms of hypoglycemia before their BG concentration falls below 70 mg/dL (3.9 mmol/L). Events with BG  $\leq$ 70 mg/dL should not be categorized as relative hypoglycemia.
  - **Probable Symptomatic Hypoglycemia:** an event during which symptoms are present, but BG measurement was not reported.
  - **Overall (or Total) Hypoglycemia:** this category combines all cases of hypoglycemia (documented hypoglycemia and probable symptomatic hypoglycemia, including severe hypoglycemia) excluding the events of relative hypoglycemia. Nocturnal and severe hypoglycemia are special cases of documented or probable hypoglycemia. If an event of hypoglycemia falls into multiple subcategories, the event is only counted once in this category.

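### The rule for merging hypoglycemia records ranks symptoms above glucose, so some documented and <54 mg/dL events go uncounted

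*SAP*

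**What the plan says.** SAP 6.11.7.1 has two merging rules. The first works through links that the patient enters in the diary: "set of events is counted as 1 event in analysis if it consists of an originating event and subsequent continuing events". The second works by time: records also merge when "the duration between adjacent events is ≤ 30 minutes". One record then stands for the set: "The event with the highest severity will be selected for analysis with severity determined in the order of" severe status first, then "2) it has symptoms of hypoglycemia reported, and 3) it has the lowest blood glucose value". Further tie-breaks (completeness of the nocturnal and post-meal answers, then latest entry) apply only "If there are multiple events tied in all 3 aspects", so the order is strictly hierarchical.

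The categories counted afterwards are set mainly by glucose. In the same section, documented hypoglycemia, including its asymptomatic and unspecified forms, "will be based on blood glucose (BG) ≤ 70 mg/dL". The section continues: "In addition, documented clinically significant hypoglycemia with similar criterion as above documented hypoglycemia", with a threshold of <54 mg/dL. Footnote a of Table ITSI.6.6 applies both thresholds to all documented hypoglycemia and its subcategories, except the post-meal analyses, which use <=70 only.

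Protocol 9.4.1 supplies two further definitions. A symptomatic event with no reported glucose is probable symptomatic, not documented. A non-severe symptomatic event above 70 mg/dL is relative, and the Overall category is formed "excluding the events of relative hypoglycemia". The same section says that events at or below 70 mg/dL do not belong in the relative category.

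**The concern.** The selection rule and the endpoint definitions pull in different directions. All Documented and the <54 category ask whether a low value was measured, with or without symptoms. The selection rule can discard that value in favour of a milder symptomatic one, or of a symptomatic record with no value at all.

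Such sets are plausible here. Protocol 5.1 requires CGM alerts to be on and asks patients to confirm hypoglycemia by SMBG. A low value can therefore be recorded before symptoms appear and checked again soon afterwards.

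At stake are the reported rates and incidences of documented and clinically significant hypoglycemia, safety measures that the SAP undertakes to report for both insulins.

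**Working it through.** The plan states no figure for this rule, so there is none to reproduce. The check applies the stated order to example sets and classifies the kept record by SAP 6.11.7.1 and Protocol 9.4.1.

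**Rule as applied.** Sort the records of a set by severe (yes first), then symptoms (yes first), then glucose (lowest first). Keep the first record. A missing glucose is taken to rank last at the third step; the SAP does not say so.

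| Records in the set (mg/dL) | Record kept | <=70 counted | <54 counted |
|---|---|---|---|
| asymptomatic 50 + symptomatic 65 | 65 | yes | **lost** |
| asymptomatic 50 + symptomatic, no glucose | no glucose | **lost** (probable symptomatic) | **lost** |
| asymptomatic 60 + symptomatic, no glucose | no glucose | **lost** (probable symptomatic) | not applicable |
| severe, no glucose + asymptomatic 50 | severe | **lost** (still counted as severe) | **lost** |
| asymptomatic 50 + symptomatic 75 | 75 (relative), if relative records enter the merge | **lost**, also from Overall | **lost** |
| asymptomatic 65 + symptomatic 75 | 75 (relative), same condition | **lost**, also from Overall | not applicable |
| symptomatic 48 + asymptomatic 66 | 48 | yes | yes |
| symptomatic 50 + symptomatic 65 | 50 | yes | yes |
| asymptomatic 50 + asymptomatic 65 | 50 | yes | yes |

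**Condition for a loss.** The kept record comes from the highest-ranked class present in the set. A <54 event is lost when the set holds a value below 54 but the kept record has glucose >=54 or none. In a set with no severe record, this means that every value below 54 lacks symptoms and the kept record is symptomatic. The event drops out of All Documented only when the kept record has no glucose or has glucose above 70.

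**Against set-level glucose.** If each set is classified by its lowest non-missing value, the first six rows are all counted at <=70, and the four that contain a 50 are also counted at <54. The number of merged sets does not change.

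**Size, under assumption only.** Let q be the share of sets with a value <54 that lose that classification. The documents give no q. Observed rate / true rate = 1 - q:

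- q = 2%: 0.98
- q = 5%: 0.95
- q = 10%: 0.90
- q = 20%: 0.80

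The observed treatment rate ratio is the true ratio times (1 - q for LY900014)/(1 - q for insulin lispro). Equal q gives a factor of 1. With 10% against 20%, the factor is 0.90/0.80 = 1.125; with the shares reversed, 0.80/0.90 = 0.889.

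**The case against.** The strongest defence is that ranking symptoms first suits the endpoints the study names. Exploratory objectives 9 and 10 are the only non-severe diary-hypoglycemia objectives, and both concern documented symptomatic events. The <54 threshold appears in no objective. For a symptomatic endpoint, taking glucose and timing from the symptomatic record is reasonable. This stands, and it is why the present selection should be kept for those endpoints. It does not justify using the same record for categories that include asymptomatic events.

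It is also fair to object to a full repair that takes any symptom together with the lowest glucose. That would call a set documented symptomatic when its only symptomatic record had no glucose, or had 75 mg/dL, and so could inflate objectives 9 and 10. This stands too.

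CGM episodes (SAP 6.12 and 9.7) are derived independently of the diary and are a partial safeguard. Their thresholds are <50, <60 and <=70 mg/dL, so none matches 54, and they do not replace the diary categories.

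Several stronger readings are tempting but not supported:

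- **Every set with mixed symptom status is misclassified.** It is not: symptomatic 48 with asymptomatic 66 loses nothing, nor does a set whose values all fall on the same side of each threshold.
- **A percentage loss can be stated.** Multiplying an assumed share of multi-record sets by an assumed share with mixed symptoms gives a share of all sets, not of sets with a value <54, and the documents supply neither share.
- **Documented events certainly turn into relative ones.** This holds only if relative records are still present at merging, and the SAP does not state the order.
- **Post-meal events move to later windows.** The kept record can carry a different post-meal answer, so a shift is possible, but it has not been shown. Post-meal analyses use <=70 only, so the <54 loss cannot reach them.

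**Conclusion.** The concern holds in a limited form. As written, SAP 6.11.7.1 undercounts <54 mg/dL events whenever the kept record hides a lower value from a lower-ranked record. It undercounts All Documented events whenever the kept record has no glucose. Both follow directly from the text. The route through relative records, which would also remove the event from Overall and run against Protocol 9.4.1, depends on an unstated order of steps.

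The affected analyses are exploratory: All Documented, Nocturnal and Daytime at both thresholds. The post-meal documented asymptomatic analysis is also exposed when the kept record has no glucose. The primary endpoint is untouched. So is the count of severe events, because severe status ranks first. A patient's <54 incidence changes only if all of that patient's <54 events are lost.

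The size cannot be given; the factors of 0.98 to 0.80 above only illustrate q from 2% to 20%. A reader might infer that the comparison of the insulins is biased. In this blinded crossover that follows only if the loss differs by insulin, and the documents give no evidence or direction for such a difference. What is established is that the reported rates can be too low.

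**What to change.** In SAP 6.11.7.1:

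1. For glucose-defined categories that do not depend on symptoms (All Documented, Nocturnal and Daytime, at <=70 and <54 mg/dL), classify each merged set by its lowest non-missing glucose.
2. Keep the present record selection for the documented symptomatic endpoints (objectives 9 and 10). Add any symptom plus lowest glucose as a sensitivity analysis only.
3. Remove relative records (symptomatic, non-severe, above 70 mg/dL) before merging, and say so.
4. State that a record with missing glucose does not displace a measured value.

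The cost is SAP wording and a little extra derivation code; no new data are needed. The drawback is that the symptomatic and the all-documented <54 counts may draw on different records of the same set, which a table footnote can explain. Overall still counts each set once, as Protocol 9.4.1 already provides.

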6.11.7.2. Systemic Hypersensitivity Reaction

The number and proportion of patients experiencing treatment-emergent potential systemic hypersensitivity reactions will be summarized and compared by treatment group using Prescott's exact test. The following Standardised MedDRA Query (SMQ) will be used to identify potential systemic hypersensitivity reactions from all TEAEs:

- Anaphylactic reaction (SMQ). Besides using the narrow and broad terms designated within the SMQ, the following search algorithm will also be implemented as another approach to determine if a patient had an anaphylactic reaction: if a patient (had at least 1 event in Category A) or (had at least 1 event that is in category B and also had at least 1

event that is in category C) or (had at least 1 event that is in category D and [also had at least 1 event in category B or at least 1 event in category C])

- Angioedema (SMQ)
- Hypersensitivity (SMQ)

Specifically, the following need to be performed: (1) any narrow or algorithmic term from any 1 of the 3 SMQs indicated above (that is, combined search across narrow and algorithmic portions of all 3 SMQs); (2) any narrow scope term within each SMQ, separately (that is, narrow SMQ search); (3) any term within each SMQ, separately (that is, broad SMQ search); (4) narrow scope term search within each SMQ, report the PT nested within each SMQ.

A similar summary will be provided for the TEAE reported by the investigator as possibly related to study drug.

Note that an individual patient may contribute multiple events. Also, a single event may satisfy multiple SMQs, in which case the event contributes to every applicable SMQ.

6.11.7.3. Infusion Site Reaction

The infusion site reactions will be searched by MedDRA PTs from all TEAEs. The number and percentage of patients experiencing at least one treatment-emergent infusion site reaction will be summarized and compared by treatment group using Prescott's exact test.

For infusion site reactions identified by MedDRA PTs, the presence and severity of erythema, induration, pain, pruritus and edema are collected on the eCRF, and will be summarized for each treatment. There will be no statistical comparison between treatments.

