5.1. Summary of Study Design

Study I8B-MC-ITSI is a Phase 3, prospective, randomized, double-blind, outpatient, multinational, multicenter, 2-treatment group, crossover, active-controlled study conducted in patients with type 1 diabetes (T1DM) currently using CSII. In the 2 treatment groups, LY900014 and insulin lispro, meal bolus doses will be delivered immediately prior to each meal (0 to 2 minutes) in a double-blind manner.

The study includes a 1-week screening period and a 2-week lead-in period followed by a 2-period (Period I and Period II) crossover and a 4-week post-treatment safety follow-up. Each period of the crossover will consist of 6 weeks of treatment with no washout between periods.

Figure ITSI.5.1 illustrates the study design.

[figure not shown]

Figure ITSI.5.1. Illustration of study design for Clinical Protocol I8B-MC-ITSI.

Patients who need to discontinue from study treatment will also be discontinued from the study. Please refer to Protocol Sections 8.1 and 8.2. In this document, discontinuation of IP refers to the last dose of IP in a study period (lead-in, Period I, or Period II).

The eCOA diary will be used by patients to document 4-point SMBGs (consists of fasting [pre-morning meal], pre-midday meal, pre-evening meal, and pre-bedtime), hypoglycemia, and all infusion set changes, including date and time of change, designation of routine or premature change, primary reason for premature change (infusion set kinked, came out, or leaking; empty

pump reservoir; infusion site pain or redness; pump occlusion alarm; suspected infusion set occlusion; other) as depicted in Protocol 9.1.4.1. Additional data on infusion site complications will be collected by investigators.

Patients will enter all non-meal-related correction boluses into the eCOA diary. In the case of suspected infusion set occlusion, patients will choose or enter a new correction bolus from the eCOA diary that corresponds to the time of the suspected occlusion. They will then indicate if the correction bolus was given via pump or via syringe. If more than one correction bolus is given, patients should choose the first non-meal related correction bolus. This information is also critical in order to evaluate the primary objective of the study.

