5.2. Determination of Sample Size

Approximately 48 patients (24 patients in each treatment sequence) will be randomized in order that approximately 42 patients complete the study.

The primary objective of this study is to compare LY900014 and insulin lispro with respect to the rate (events/patient/30 days) of infusion set failures that lead to premature infusion set changes, due to a pump occlusion alarm OR due to unexplained hyperglycemia with blood

glucose (SMBG) >250 mg/dL (13.9 mmol/L) that does not decrease within 1 hour following a correction bolus delivered via the pump, during the 6-week treatment period.

The study was designed following a regulatory interaction to assess the safety comparability of LY900014 and insulin lispro. It is not designed or powered to be a non-inferiority or superiority trial.

Assuming a 12% dropout rate after randomization, approximately 48 patients (24 patients in each treatment sequence) will need to be randomized.

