Unless otherwise noted, all tests of treatment effects will be conducted at a 2-sided alpha level of 0.05, and confidence intervals (CIs) will be calculated at 95%, 2-sided. If conducted, all tests of interactions between treatment groups and other factors will be conducted at a 2-sided alpha level of 0.10.

The definitions of baseline and post-baseline for the safety and efficacy analyses depend on which analysis period is being used. The following analysis periods will be used:

- Lead-in Period – Visits 2-3
- 12-Week Treatment Period while on IP – from first dose to last dose of IP in each 6-week randomized treatment period (Period I and Period II)
- 12-Week Treatment Period Regardless of IP use – from randomization to Week 6 of each randomized treatment period (including all data regardless of IP use)
- Safety Follow-up Period – Visit 801

Table ITSI.6.2 describes the rules for determining the patient population, baseline and postbaseline observations for the different analysis periods. The data in the lead-in and the safety follow-up visit, if summarized, will be for overall, not by treatment group.

The data on IP is defined based on the following rules:

- for data only measured at an office visit (for example, HbA1c), if the office visit date (or laboratory sample collection date) is within 14 days of the date of last study drug dose of the randomized treatment period (Period I or Period II), then postbaseline data measured at or prior to that office visit will be considered as data on IP.
- for data collected as running records with an exact date and/or time stamp such as diary entries where the date and time of the measures was not tied with the date of an office visit, postbaseline data with date and time \leq (last study drug dose date and time) will be considered as data on IP.

For continuous measures, summary statistics will include sample size, mean, standard deviation (SD), median, minimum, and maximum for both the actual and the change from baseline measurements. Least squares (LS) means and standard errors derived from the analysis models will also be displayed for the change from baseline measurements. Treatment comparisons will be displayed showing the treatment difference LS means and the 95% CIs for the treatment differences, along with the p-values for the treatment comparisons.

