6.11.2. Other Secondary Safety Analyses

The analyses described in Section 6.11.2 will include data collected for the Safety Population including data collected prior to permanent discontinuation (i.e., last dose) of IP in each 6-week treatment period. In addition, other than severe hypoglycemia events, all secondary safety endpoints are pump-related, and therefore the corresponding analyses will also exclude data (if any) that are collected while patients temporarily are off pump or off IP.

For the following secondary safety endpoints, the incidence (percent of patients with at least 1 event) and rate will be analyzed using Prescott's exact test and Wilcoxon signed-rank test, respectively, as described above for the primary endpoint.

- suspected infusion set occlusions defined as unexplained hyperglycemia with blood glucose (SMBG) >250 mg/dL (13.9 mmol/L) that does not decrease within 1 hour (+10 minutes) following a correction bolus delivered via the pump and that leads to an infusion set change
- infusion set failures leading to premature infusion set changes due to unexplained hyperglycemia with blood glucose >250 mg/dL that does not decrease by >50 mg/dL within 1 hour (+10 minutes) following a correction bolus delivered via the pump
- premature infusion set changes for any reason and for each individual reason (infusion set kinked, came out or leaking; empty pump reservoir; infusion site pain or redness; pump occlusion alarm; suspected infusion set occlusion; other)
- severe hypoglycemic events

For the infusion set failures and premature infusion set changes, the number of events and the number of patients with events will be derived for each treatment group by infusion set catheter dwell time (≤ 24 hours, >24 and ≤ 48 hours, >48 and ≤ 72 hour, >72 hours), and overall (across over the course of approximately 72-hours of continuous infusion).

A listing of premature infusion set changes due to unexplained hyperglycemia will be generated. For each premature infusion set change due to unexplained hyperglycemia, the following information will be provided:

- whether it is an infusion set failure that meets the primary endpoint definition

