^a In extremely rare cases where patients stopped treatment on pump but continued to use treatment through syringe until they discontinue from the study, the last dose form will capture the timing of the last dose of treatment in CRF, which will not be the last infusion set change.

The last infusion set change in each treatment period (lead-in, Period I or Period II) occurs only when a patient comes to an office visit or early discontinuation of study treatment. This change is not reflective of patients' behavior regarding infusion set changes, and thus it will not be included in the derivation of time until infusion set changes. Patient-reported premature infusion set changes due to the reason "Other" or patient-reported routine infusion set changes that occur within 1 hour of a previous infusion set change (captured in the case report form [CRF]), will be treated as a redundant entry in eCOA and excluded from all analyses. In addition, any patient-reported routine infusion set change that occurred within 24 hours of a previous infusion set change could have been misreported as routine or are redundant entries in eCOA, and thus will be excluded from all analyses.

Time interval until infusion set change for each infusion set can be derived through a minute-to-day conversion by dividing the time difference between the infusion set change and its previous infusion set change by 1440 minutes. The protocol requires that patients change infusion set every 72 ± 4 hours unless a change is required for failure of the infusion set. To handle potential missing input in eCOA for the infusion set change, time interval until infusion set change greater than 7 days (168 hours) will be excluded. For each treatment period, time interval until infusion set change will be derived by averaging all infusion set changes within the period. The analyses will be conducted by an MMRM model (Model 2) as specified in Section 6.1.

Derivation and analysis of interstitial glucose reduction rate are described in Section 6.12.

Actual and change from baseline in total, basal, and bolus insulin doses and bolus/total insulin dose ratios will be compared between LY900014 and insulin lispro using an MMRM model (Model 1) as specified in Section 6.1. The doses and bolus/total insulin dose ratios for each visit will be calculated as the mean of the doses for the last 3 days prior to the visit. A listing of insulin doses will also be provided, including data collected at Visit 801.

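### Infusion site reactions coded as adverse events are tested only as at least one per patient and treatment, which discards recurrence over about 14 sites per period; a rate comparison would be a cheap exploratory addition

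*SAP*

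**What the plan says.** SAP 6.11.7.3 finds infusion site reactions by MedDRA preferred term among the treatment-emergent adverse events. Its one treatment comparison is that "patients experiencing at least one treatment-emergent infusion site reaction will be summarized and compared by treatment group", with Prescott's exact test. The symptoms and severity recorded for each reaction are tabulated by treatment without a test. No rate is planned for these reactions.

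For the pump events in SAP 6.11.2 (suspected occlusions, set failures, premature set changes by reason) and for severe hypoglycemia, "the incidence (percent of patients with at least 1 event) and rate will be analyzed using" Prescott's test and the Wilcoxon signed-rank test respectively. SAP Table ITSI.6.6 likewise plans both incidence and rate for the other hypoglycemia categories.

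Two other passages touch site reactions. In SAP 6.11.2, infusion site pain or redness is one of the reasons for a premature set change, and that reason is compared as a rate. SAP 6.16 lists event numbers per preferred term and treatment for the registry, without a test.

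**The concern.** A site reaction can recur at every new set. "The protocol requires that patients change infusion set every 72 ± 4 hours unless a change is required for failure of the infusion set", and "Each period of the crossover will consist of 6 weeks of treatment with no washout between periods", so each insulin is exposed to about 14 sites per patient. A yes/no score cannot tell one reaction from several. A patient with 2 reactions on lispro and 4 on LY900014 is a concordant pair and gives Prescott's test no evidence of a difference.

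At stake is local tolerability. Protocol 3.2 describes treprostinil in LY900014 as an excipient that acts by local vasodilatation, so reactions at the infusion site are a formulation-specific question. If reactions cluster in some patients, the planned test could show little difference although those patients react much more often. The SAP gives no reason for treating these events differently from its other repeatable events.

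**Working it through.** **Inputs from the documents.** Testing: "all tests of treatment effects will be conducted at a 2-sided alpha level of 0.05" (SAP 6.1). Size: "Approximately 48 patients (24 patients in each treatment sequence) will be randomized in order that approximately 42 patients complete the study" (SAP 5.2). The plan's own figure reproduces: 42 / (1 − 0.12) = 47.7, rounded up to 48. No power, reaction rate or effect size is given for site reactions, so no power figure can be reproduced.

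**Sites per period.** 42 days / 3 days = 14. At 76 and 68 hours, 1,008 / 76 = 13.3 and 1,008 / 68 = 14.8, before any premature changes.

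**Share of ties.** Assume 14 independent sites, a mean of m reactions per period on lispro and 2m on LY900014. A prone patient reacts in both periods with probability

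[1 − (1 − m/14)^14] × [1 − (1 − 2m/14)^14].

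- m = 0.15: 4%
- m = 1: 0.646 × 0.884 = 57%
- m = 2: 0.884 × 0.991 = 88%
- m = 3: 97%

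With 42 completers, Prescott's test cannot reach p < 0.05 with fewer than five discordant patients all in one direction: four give p = 0.107 at best, five give 0.048 at best. With 13 prone patients at m = 2, only about 13 × (1 − 0.88) = 1.6 are expected to be discordant.

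**Simulation 1: only prone patients react.** 42 completers, 21 per sequence, true doubling on LY900014.

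| Prone patients | Lispro mean per period | Prescott, yes/no | Signed-rank, counts |
|---|---|---|---|
| 8 | 1 | 1% | 21% |
| 8 | 2 | 0% | 52% |
| 13 | 1 | 11% | 48% |
| 13 | 2 | 0.3% | 85% |
| 21 | 1 | 29% | 75% |
| 21 | 2 | 3% | 98% |
| 21 | 0.15 | 9% | 9% |
| 42 (all) | 1 | 65% | 98% |

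With 4 prone patients neither test can reach significance. With extra period-to-period variation (gamma variance 0.3) and 13 prone patients, the count test falls to 34% to 63% over lispro means of 1 to 3; Prescott's is 0% to 8%.

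**Simulation 2: everyone else also reacts occasionally.** Poisson counts, others at 0.05 against 0.10 per period. The ranges cover repeated independent runs.

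| Assumption | Prescott | Signed-rank |
|---|---|---|
| 30% prone, 2 vs 4 | 8–9% | 74–77% |
| 40% prone, 2 vs 4 | 11–13% | 87–90% |
| All patients, 0.5 vs 1.0 | 50–51% | 73–75% |
| 30% prone, 0.3 vs 0.6 | 13% | 21% |

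In the first row the expected incidence is 0.3 × (1 − e^−2) + 0.7 × (1 − e^−0.05) = 29% on lispro and 0.3 × (1 − e^−4) + 0.7 × (1 − e^−0.10) = 36% on LY900014, so a doubling of events shows as 7 percentage points. With no true difference the signed-rank test rejects in about 4% to 5% of runs.

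**Effect of the treatment-emergent rule.** Under SAP 6.11.5 and Table ITSI.6.2, the lead-in is the baseline, and an event of the same lowest level term and no greater severity is not treatment-emergent. At 2 reactions per 42 days, the chance of at least one in a 14-day lead-in is 1 − exp(−2 × 14/42) = 49%. If those patients drop out of the count (one term, constant severity), the first three rows become 5% vs 44%, 5% vs 58% and 41% vs 65%. Adding the variance of 0.3, the count test has 31% and 38% in the first two rows. Exact signed-rank p-values took several points off the first two lead-in count figures and left the ordering unchanged.

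**The case against.** The strongest reply is that this is ordinary adverse event reporting. Protocol 10.3.3.2 specifies patients with at least one event, compared by Prescott's test, and adverse events are an exploratory objective. The SAP treats systemic hypersensitivity in the same way. The trial also says of itself: "It is not designed or powered to be a non-inferiority or superiority trial". That stands: the SAP follows the protocol, and low power in an exploratory safety test is not an error in itself. The point is only that a comparison already planned discards usable information.

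Three stronger readings are tempting, and the documents do not support them.

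- **That site reactions are compared only as yes/no anywhere in the plan.** Set changes for infusion site pain or redness are compared as a rate, and event numbers go to the registry. But the first covers only reactions that ended a set early and does not name pruritus, induration or edema. The second is untested and unpaired.
- **That a doubling is in general almost undetectable.** This holds for a minority reacting about twice or more per period. With all patients at a mean of 1, Prescott's test has about 65% power. For rare reactions both tests are equally weak.
- **That the counts are already in hand.** Protocol 9.2 has sites record new conditions and changes in conditions. Nothing says that each affected site is a separate record. If recurrent redness is entered as one continuing event, a rate reflects recording style, and SAP 6.11.5 would count it in the first period only.

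**Conclusion.** The point holds as a cheap improvement to an exploratory analysis. For adverse-event-coded site reactions, the single planned test ignores recurrence over about 14 sites per period, unlike the SAP's handling of its other repeatable events. If 30% to 40% of patients are prone with means of 2 against 4, power is about 8% to 13% for the planned test against 74% to 90% on counts, or about 5% against 44% to 58% once the lead-in rule removes prone patients. The upper figures are best cases. All of this rests on assumed rates and clustering, because the documents give neither; with rare reactions the gain is small or nil. It also assumes that recurrent reactions are recorded as separate events.

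**What to change.** In SAP 6.11.7.3 keep the incidence and Prescott's test, and add:

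- infusion site reactions per patient per 30 days, compared by the Wilcoxon signed-rank test used in SAP 6.11.2, and the total number of reactions per treatment;
- a counting rule: each new reaction with its own start date is one event, with a statement of whether each affected site is recorded as a separate adverse event;
- one time base for numerator and denominator: either events on study insulin over the exposure of SAP 6.11.1, or all events over the full period length. Mixing them would not work, because SAP 6.1 counts adverse events regardless of study drug use while 6.11.1 exposure excludes interruptions;
- how the lead-in-severity and continuing-event rules apply to recurrent reactions.

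The cost is a few SAP sentences and one table, with no new visits or patients. The downsides are one more unadjusted safety comparison and a gain that depends on how recurrent reactions were recorded.
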